4.10.4. Sensitivity Analyses for the Primary Efficacy Endpoint

The following sensitivity analyses of the primary and secondary efficacy endpoints will be performed to assess the robustness of the analyses across endpoints:

a) The primary efficacy endpoint analysis performed on the PP population

The primary efficacy endpoint analysis, as defined in [Section 4.10.1](#) will be performed using the PP Population

b) The primary efficacy endpoint analysis performed on the Randomized population

The primary efficacy endpoint analysis, as defined in [Section 4.10.1](#) will be performed using the Randomized Population (note: this includes randomized patients on eteplirsen)

c) ANCOVA on the primary efficacy endpoint using MAR, MNAR, and OC

The primary efficacy endpoint, the CFB in the NSAA Total Score at Week 52 will be analyzed by an ANCOVA model. The ANCOVA model will include CFB in the NSAA Total Score at Week 52 as the dependent variable, treatment and region (North America vs. Europe/Asia/Australia) as factors, and baseline age (as a continuous variable), baseline time

to stand from supine (as a continuous variable), and baseline NSAA score (as a continuous variable) as covariates.

Three different methods of addressing missing data will be performed:

- 1) **Missing at Random (MAR)** Missing data will be imputed using the MAR algorithm described in [Section 4.10.6.1](#).
- 2) **Missing Not at Random (MNAR)** Missing data will be imputed using the MNAR algorithm described in [Section 4.10.6.2](#).
- 3) **OC (Observed Case)** this ANCOVA will be performed on non-missing data.

These analyses will be performed on the FAP.

d) Observed Week 52 MMRM

The primary efficacy endpoint analysis will be repeated (i.e., as described in [Section 4.10.1](#)) subset to those patients who had a non-missing CFB value at Week 52.

e) MMRM with multiple imputation assuming MAR

The primary efficacy endpoint analysis will be repeated (i.e., as described in [4.10.1](#)) with missing data imputed based on a Missing at Random (MAR) pattern as described in [4.10.6.1](#).

f) MMRM with multiple imputation assuming MNAR

The primary efficacy endpoint analysis will be repeated (i.e., as described in [4.10.1](#)) with missing data imputed based on a Missing Not at Random (MNAR) pattern as described in [4.10.6.2](#)

g) Including siblings

The primary efficacy endpoint analysis will be repeated (i.e., as described in [4.10.1](#)) including the siblings in the FAP.

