2.2. Randomization Methodology

Patients will be randomized 2:1 to receive edasalonexent or placebo in a double-blind fashion. Randomization will be stratified by Baseline age (≤ 6.0 vs. > 6.0 years), baseline time to stand

from supine (≤ 5 vs. > 5 seconds), treatment with eteplirsen (yes vs. no), and region (North America vs. Europe/Asia/Australia). Note that if siblings are enrolled, they will be assigned to the same treatment group.

Any mis-categorization of a patient's randomization strata (i.e., a patient being assigned to an incorrect randomization strata relative to their actual study data) will be presented in a listing. Analyses by strata (i.e., see [Section 4.10.8](#)) will be based on the randomization strata values.

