3. PATIENT POPULATIONS

3.1. Population Definitions

The following patient populations will be evaluated and used for presentation and analysis of the data:

- Randomized Population: all patients who are randomized into the study with patients to be analyzed based on the study treatment they were randomized to.
- Safety Population: all patients who receive at least one dose of study drug with patients to be analyzed based on the actual study treatment received.
- Full Analysis Population (FAP): all patients in the Randomized Population who receive at least one dose of study drug and provide at least one non-missing post-Baseline NSAA efficacy assessment.
 - Note that the FAP will exclude patients on eteplirsen at randomization and patients will be analyzed based on the study treatment they were randomized to.
- Per Protocol (PP) Population: all patients in the FAP who complete the 52-week treatment period of the study without any significant protocol deviations with patients to be analyzed based on the study treatment they were randomized to.

The set of patients in the Per Protocol population may be updated due to study drug compliance information which will not be collected until after database lock and unblinding due to the COVID-19 pandemic, see [Section 3.2](#).

note: the variable to determine a patient completing the 52-week treatment period is from the End of Study eCRF page “Did subject complete the study?” = Yes.

The FAP will be the primary population for the analysis of efficacy parameters. The Safety Population is the primary population for the analysis of safety endpoints.

Note that if siblings are enrolled, only one sibling will be included in the Randomized Population. This is to avoid having siblings being randomized to different study medications, increasing the risk a subject will inadvertently take incorrect study medication. The second sibling will be assigned to the same treatment group as the randomized sibling. If both siblings meet the inclusion/exclusion criteria, the sibling to be included in the Randomized Population will be the first sibling randomized, both siblings will be included in the Safety Population (see [Section 3.1](#)). The sibling not included in the Randomized Population will have their data presented in the listings and will be included in some of the sensitivity analyses.

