4.2.4. Adjustments for Covariates

Statistical models will adjust for the stratification variables as covariates.

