4.10.1. Primary Efficacy Analysis

The primary efficacy endpoint is the CFB in the NSAA Total Score at Week 52. NSAA Total Scores and the CFB values will be summarized by treatment group and time point using descriptive statistics.

If a patient initiates corticosteroid therapy or discontinues study treatment, all observations from that patient after these events will be censored from the primary efficacy analyses.

The primary efficacy endpoint analysis will be an MMRM ANCOVA. The MMRM model will include:

- CFB in the NSAA Total Score as the dependent variable
- Variables in the Model

Visit (a categorical variable)	
Treatment (edasalonexent or placebo)	Treatment \times Visit
Region (North America vs. Europe/Asia/Australia)	Region \times Visit
Baseline age (as a continuous variable),	Baseline Age \times Visit
Baseline time to stand from supine (as a continuous variable)	Baseline time to Stand \times Visit
Baseline NSAA score (as a continuous variable)	Baseline NSAA score \times Visit

- Patient as a random effect.

The primary efficacy analysis will test the difference between the edasalonexent versus placebo at Week 52 using this MMRM model.

Sample SAS code for the primary efficacy analysis is provided in [APPENDIX 1: Sample MMRM Code](#).

Descriptive summary statistics including number of patients, mean, standard error, least-square means (LS means), LS means differences, along with the p-values and corresponding 95% CIs

will be provided. Specifically, the primary efficacy endpoint hypothesis test of no treatment difference between edasalonexent and placebo is based on the least-squares means (LS-means) difference and corresponding p-value from the Week 52 visit. The results for the treatment difference for the other visits will also be provided to assess the consistency of treatment effect over different visits.

The repeated-measures analysis will be based on the restricted maximum likelihood method assuming an unstructured covariance structure to model the within-patient errors. A Kenward-Roger approximation will be used for the denominator degrees of freedom. If there is a convergence problem due to the unstructured covariance matrix, a compound symmetry covariance structure will be used to model the within-patient variance; if the compound symmetric covariance structure fails to converge, a variance components approach will be applied.

The primary efficacy endpoint analysis is an observed case analysis, with no imputation of missing data.

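### The Randomized Population sensitivity analysis readmits eteplirsen patients but reuses a model with no eteplirsen term, leaving out a randomisation stratum that SAP 4.2.4 says is adjusted for; the cost is a little precision.

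*SAP*

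**What the plan says.** - **Randomisation.** SAP 2.2 (and protocol 5.5.1) stratifies by age, time to stand, "treatment with eteplirsen (yes vs. no), and region".
- **General rule.** SAP 4.2.4 consists of one sentence with no exceptions: "Statistical models will adjust for the stratification variables as covariates".
- **Primary model.** SAP 4.10.1 lists visit, treatment, region, baseline age, baseline time to stand and baseline NSAA. Each of the last five is crossed with visit. Eteplirsen is not listed.
- **Primary population.** SAP 3.1 states: "Note that the FAP will exclude patients on eteplirsen at randomization".
- **Sensitivity analysis (b).** SAP 4.10.4 applies the 4.10.1 analysis, as defined there, to the Randomized Population, with the remark "note: this includes randomized patients on eteplirsen". It adds no model term.
- **Secondary endpoints.** SAP 4.10.5 applies the 4.10.4 analyses to the three timed function tests.
- **Declared changes.** SAP section 6 records the move to continuous covariates and the visit interactions. It declares no exception to 4.2.4.

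**The concern.** Leaving eteplirsen out of the primary model is coherent, because the factor is constant in that population. In (b) it is not constant, and the SAP says so in the same sentence that carries the model over.

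The omission touches what distinguishes (b) from the primary analysis. An observed-case MMRM takes nothing from a boy with no post-baseline score. For the NSAA, the eteplirsen boys are therefore essentially the only data that (b) adds. For the timed tests, a boy without a valid NSAA total could also enter, but that is marginal.

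If boys on eteplirsen progress differently, two things follow. The difference sits in the residual variance and widens the confidence interval. Any departure from 2:1 within the stratum, by chance or through dropout, also passes into the treatment estimate uncorrected. A programmer has two instructions as well, since 4.2.4 and 4.10.4(b) imply different models.

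**Working it through.** **Inputs from SAP 4.1.** N = 126, 2:1 (84 and 42); SD 4.8; difference 3.0; dropout about 20%; two-sided 0.05.

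**The plan's own figures.** 3.0 / 4.8 = 0.625, as stated. The stated 126 and 80% are not reproduced exactly. The normal approximation needs 31 + 62 = 93 evaluable, and 93 / 0.8 rounds up to 117. With 126 × 0.8 = 100.8 evaluable, power is 84.1%. The gap is on the safe side and does not bear on this point.

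**Assumptions.** The documents give no eteplirsen share; protocol 9.2 only says it should not exceed representation in the Duchenne population. They give no prognostic effect either. I take a share p of 2% to 13% (126 × 0.02 = 2.5 to 126 × 0.13 = 16.4 boys) and a shift g of 1 to 3 NSAA points (1/4.8 = 0.21 SD to 3/4.8 = 0.625 SD).

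**Loss of precision.** Without the term, residual SD = √(4.8² + p(1 − p)g²). Dividing by 4.8 gives the standard-error ratio:

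| p | g = 1 | g = 2 | g = 3 |
|---|---|---|---|
| 2% | 1.0004 | 1.0017 | 1.0038 |
| 5% | 1.0010 | 1.0041 | 1.0092 |
| 10% | 1.0020 | 1.0078 | 1.0174 |
| 13% | 1.0025 | 1.0098 | 1.0219 |

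The largest cell is √(1 + 0.13 × 0.87 × 9 / 23.04) = 1.0219. With 101 completers, power is 82.6% to 84.1% without the term and 84.2% with it. The formula ignores what region, age, time to stand and baseline NSAA already absorb, so it tends to overstate the loss.

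**Imbalance.** Suppose one eteplirsen boy more than the exact 2:1 split is on active and one fewer on placebo. The estimate then moves by g × (1/84 + 1/42) = 0.0357g, which is 0.04 points at g = 1 and 0.11 at g = 3. The latter is 0.107 / 3.0 = 3.6% of the planned difference.

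**Type I error.** I simulated 126 boys, 2:1 in blocks of 3 within eteplirsen strata, with a single-time ANCOVA and 4,000 runs per scenario. Block size is an assumption. The other three strata and dropout were not modelled. Simulation error is about 0.35 percentage points.

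| p, g | Rejection without term | Rejection with term |
|---|---|---|
| 5%, 2 | 4.6% | 4.8% |
| 10%, 2 | 5.3% | 5.7% |
| 10%, 3 | 4.8% | 5.2% |
| 13%, 3 | 4.9% | 5.2% |

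Omission does not inflate the error rate. At p = 13%, g = 3 the simulated standard errors are 0.9251 and 0.9052, a ratio of 1.022, which agrees with the formula.

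**Parameters needed.** The 4.10.1 model crosses every covariate with visit over Weeks 13, 26, 39 and 52. A parallel eteplirsen term costs 1 main effect + 3 interaction parameters = 4.

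**The case against.** - **4.2.4 is a loose general statement.** The ECG and heart-rate models (SAP 4.13.5) and the NSAA item models (SAP 4.10.7) adjust for no stratum. The protocol's own model (9.10.1) omits eteplirsen while leaving the exclusion of these boys to the SAP. This stands in part: 4.2.4 also needs rewording. It does not justify (b), the one 4.10.4 analysis that deliberately brings the eteplirsen stratum back.
- **(b) should vary the population and hold the model fixed.** This is a defensible design, but the SAP does not offer it as a reason, and it conflicts with the SAP's own rule.
- **The stratum may be too small, and region is a partial proxy.** Both are possible. The first calls for a fallback. On the second, eteplirsen use can still vary within a region.
- **Sample code might differ.** SAP Appendix 1 is not in the text available to me. Section 4.10.1 describes it as code for the primary analysis, and nothing points to a variant for (b).

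A reader might also infer more than the documents support:

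- **Materially wrong standard errors.** A loss of about 5.5% needs a 13% share together with a 1.0 SD shift. That shift is 4.8 points, more than the 3.0 the trial is powered on, and the protocol's introduction describes eteplirsen's efficacy as limited.
- **A biased or error-prone main result.** The primary analysis and the tested secondary endpoints exclude these boys, and (b) lies outside the testing hierarchy in SAP 4.2.5.
- **A compromised intention-to-treat analysis.** (b) inherits the censoring in 4.10.1 after steroid start or treatment discontinuation, so it is not an intention-to-treat analysis in the usual sense.

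**Conclusion.** The inconsistency is real and minor. SAP 4.10.4(b), and its repeats under 4.10.5, leave out a randomisation stratum that varies in the population analysed, contrary to 4.2.4.

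Under the assumed ranges, the price is a standard error 0.04% to 2.2% larger and a shift of about 0.04 to 0.11 NSAA points for each boy displaced from the 2:1 split. Both results rest on the assumed share and prognostic shift. For the timed function tests, the same standard-error ratios hold only if the shift in SD units is similar, and the documents give no SD for those endpoints. There is no sign of type I error inflation, and no confirmatory conclusion depends on this.

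**What to change.** 1. In SAP 4.10.4(b) and its versions under 4.10.5, add eteplirsen (yes/no) and eteplirsen × visit, in line with the other covariates.
2. State the fallback in advance. If the stratum is too small to estimate (for example, no eteplirsen boy observed at some visit, or non-convergence), keep the main effect only, or use the 4.10.1 model and report that this was done. A main effect alone assumes the same shift at every visit and is second best.
3. Report the number of eteplirsen boys per arm beside (b). If all are in one arm, the adjusted analysis gains almost nothing from them.
4. Reword 4.2.4 to cover efficacy models in which the stratum varies, and name the 4.10.7 item models as exceptions.

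The cost is about four parameters and a few sentences. The factor is already recorded for randomisation, so no new data are needed.

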4.10.5. Sensitivity Analyses for the Secondary Efficacy Endpoints

The sensitivity analyses for the primary efficacy endpoint as defined in [Section 4.10.4](#) will be applied to the secondary endpoints.

4.10.6. Multiple Imputation Methods

As part of the sensitivity analysis, the missing CFB primary and secondary efficacy endpoints will be imputed using multiple imputation (MI) for each of the scheduled assessment visits (i.e., Weeks 13, 26, 39, and 52). Both an MAR and MNAR method will be applied.

The following random number seeds will be used for each endpoint/multiple imputation; these seeds were randomly generated.

Table 5: Random Number Seeds for Multiple Imputation

Endpoint	Random Number Seed	
	MAR	MNAR
NSAA	29068	24158

10MWT Speed	52987	60804
Stand from Supine Speed	69440	21531
4-stair Climb Speed	36875	55339

Imputation distribution:

The imputation distribution for the missing change from baseline endpoints will be a normal distribution. Although the change from baseline values are integers for the primary change from baseline in NSAA endpoint, imputed values will be rounded to 1 decimal place when used in the analysis. For the change from baseline secondary endpoints (i.e., TFT reciprocal of seconds endpoints) the imputed values will be rounded to 4 decimal places (i.e., the ten-thousandth place).

4.10.6.1. Multiple Imputation Assuming MAR

Imputation algorithm:

Missing post-baseline change from baseline values will be imputed via multiple imputation (MI) assuming MAR for each scheduled assessment visit.

Fifty imputed datasets will be created. Each of the imputed datasets will be analyzed via the specified primary or secondary efficacy endpoint analysis. The results across the multiple imputed data sets will be combined using SAS Proc MIANALZYE (sample SAS code for primary analysis provided in [APPENDIX 2: Sample Multiple Imputation Code](#)).

The following are the set of variables to be used in the multiple imputation model:

- Treatment group (edasalonexent or placebo)
- Region (North America vs. Europe/Asia/Australia)
- Baseline age (continuous variable)
- Baseline time to stand from supine (continuous variable)
- Baseline value for the endpoint being imputed (continuous variable)
- Previous change scores (e.g., for the Week 52 CFB imputation, the CFB scores at Weeks 13, 26, and 39 will be included)

The imputations will be performed using monotone linear regression imputation methods which will impute the patients' missing post-baseline change scores at each of the scheduled assessment visits in the study.

If the missing data does not follow a monotonic pattern, a sequential approach to imputing the data via a Markov chain Monte Carlo (MCMC) method to produce a monotone missing data pattern will be applied using the MCMC impute=monotone option in Proc MI (SAS System). Following the method described in [Smith \(2017\)](#) the non-monotonic data imputation will be performed “by” the categorical treatment variable (note: the categorical variable Region will not be included in the non-monotonic imputation). Then the monotone linear regression imputation methods will be applied.

Note: if the multiple imputation model does not converge or produce estimates (i.e., due to over-specification) the set of imputation variables may be modified.

4.10.6.2. MMRM with Multiple Imputation Assuming MNAR

Imputation algorithm:

For this imputation the monotonic missing post-baseline change from baseline scores will be imputed via multiple imputation assuming MNAR for each scheduled assessment visit (i.e., Weeks 13, 26, 39, and 52).

The imputation of monotonic missing scores in the edasalonexent treatment group will be based on the distribution in the placebo group. This method assumes that the trajectory of withdrawals from the edasalonexent treatment arm follows the distribution of the placebo patients. The MNAR option in Proc MI (SAS system) will be used to impute the placebo distribution as described (Yuan, 2014).

Fifty imputed datasets will be created. Each of the imputed datasets will be analyzed via the same model as the primary efficacy endpoint analysis (see Section 4.10.1). The results across the multiple imputed data sets will be combined using SAS Proc MIANALZYE (details provided in APPENDIX 2: Sample Multiple Imputation Code).

The set of variables for this MNAR multiple imputation model is the same set as defined for the MAR multiple imputation (Section 4.10.6.1), with the exception of Treatment group, which is not included in the MNAR imputation (i.e., the placebo distribution is used to impute the data).

The imputations will be performed using monotone linear regression imputation methods which will impute the patients' missing post-baseline change scores at each of the scheduled visits in the study (i.e., Weeks 13, 26, 39, and 52).

If the missing data does not follow a monotonic pattern, a sequential approach to imputing the data via an MCMC method to produce a monotone missing data pattern will be applied using the MCMC impute=monotone option in Proc MI (SAS System). Following the method described in Smith (2017) the non-monotonic data imputation will be performed "by" the categorical treatment variable (note: the categorical variable Region will not be included in the non-monotonic imputation). Then the monotone linear regression imputation methods will be applied.

Note: if the multiple imputation model does not converge or produce estimates (i.e., due to over-specification) the set of imputation variables may be modified.

4.10.7. Supportive Analyses on Primary and Secondary Efficacy Endpoints

The following analyses will be performed to support the primary endpoint analyses. These analyses will be performed on the FAP.

- NSAA Categorical Change from Baseline: The percentage of patients with a change from baseline in NSAA Total Score at Week 52 will be compared between the treatment groups. The following categories for change from baseline in NSAA will be considered
 - Improvement: $\geq 0, \geq 1, \geq 2, \geq 3, \geq 4$
 - Decline: $\leq 0, \leq -1, \leq -2, \leq -3, \leq -4, \leq -5$

The difference between the treatment groups will be compared by a chi-square test, except for the scenarios where, in either group, there are only 5 patients or less in the numerator (or, conversely, N-5 patients or more) in which case a Fisher's exact test will be used.

Additionally, a Kolmogorov–Smirnov test for differences in the change from baseline in NSAA Total Score between treatment groups will be performed.

- Increase in function in Week 52 NSAA Items: For each of the 17 NSAA items, the number and percent of patients with an increase in function will be summarized. A patient is defined as having an increase in function if the baseline items score is <2 and the post-baseline value is greater than the baseline value. Patients with a baseline item score of 2 or a missing Week 52 NSAA item value are excluded from the analysis.

For each item, the percentages, odds ratio (with 95% CI), and a p-value comparing the treatment group difference in proportions will be presented.

For the Overall NSAA increase in function, the overall odds ratio, 95% CI, and p-value will be estimated from a generalized estimating equations (GEE) model with treatment and NSAA item as class variables in the model, increase in NSAA item (i.e., a dichotomous variable) as the dependent variable, baseline item score as a covariate, and subject as the repeated term with an exchangeable working correlation matrix.

The patient count and percent of number of Week 52 NSAA items which increased in function will be presented (i.e., the “count” is the number of NSAA items with a baseline score <2 and the post-baseline value is greater than the baseline value. The percent is the “count” divided by the number of NSAA items with a baseline score <2 and non-missing Week 52 value).

- Preservation of function in Week 52 NSAA Items: For each of the 17 NSAA items, the number and percent of patients with preservation of function will be summarized. A patient is defined as having a preservation of function if the baseline items score is >0 and the post-baseline value is >0 . Patients with a baseline item score of 0 or a missing Week 52 NSAA item value are excluded from the analysis.

For each item, the percentages, odds ratio (with 95% CI), and a p-value comparing the treatment group difference in proportions will be presented.

For the Overall NSAA increase in function, the overall odds ratio, 95% CI, and p-value will be estimated from a generalized estimating equations (GEE) model with treatment and NSAA item as class variables in the model, NSAA item score >0 (i.e., a dichotomous variable) as the dependent variable, baseline item score as a covariate, and subject as the repeated term with an exchangeable working correlation matrix.

The patient count and percent of number of Week 52 NSAA items with preserved function will be presented (i.e., the “count” is the number of NSAA items with a baseline score >0 and the post-baseline value is >0 . The percent is the “count” divided by the is the number of NSAA items with a baseline score >0 and non-missing Week 52 value).

- Worsening of function in Week 52 NSAA Items: For each of the 17 NSAA items, the number and percent of patients with a worsening of function will be summarized. A patient is defined as having a worsening of function if the baseline items score is >0 and the post-baseline value is less than the baseline value. Patients with a baseline item score of 0 or a missing Week 52 NSAA item value are excluded from the analysis.

For each item, the percentages, odds ratio (with 95% CI), and a p-value comparing the treatment group difference in proportions will be presented.

For the Overall NSAA worsening in function, the overall odds ratio, 95% CI, and p-value will be estimated from a generalized estimating equations (GEE) model with treatment and NSAA item as class variables in the model, worsening of function (i.e., a dichotomous variable) as the dependent variable, baseline item score as a covariate, and subject as the repeated term with an exchangeable working correlation matrix.

The patient count and percent of number of Week 52 NSAA items with worsening function will be presented (i.e., the “count” is the number of NSAA items with a baseline score >0 and the post-baseline value is less than the baseline value. The percent is the “count” divided by the is the number of NSAA items with a baseline score >0 and non-missing Week 52 value).

- Loss in function in Week 52 NSAA Items: For each of the 17 NSAA items, the number and percent of patients with a loss of function will be summarized. A patient is defined as having a loss of function if the baseline items score is >0 and the post-baseline value is 0. Patients with a baseline item score of 0 or a missing Week 52 NSAA item value are excluded from the analysis.

For each item, the percentages, odds ratio (with 95% CI), and a p-value comparing the treatment group difference in proportions will be presented.

For the Overall NSAA loss in function, the overall odds ratio, 95% CI, and p-value will be estimated from a generalized estimating equations (GEE) model with treatment and NSAA item as class variables in the model, loss of function (i.e., a dichotomous variable) as the dependent variable, baseline item score as a covariate, and subject as the repeated term with an exchangeable working correlation matrix.

The patient count and percent of number of Week 52 NSAA items with loss of function will be presented (i.e., the “count” is the number of NSAA items with a baseline score >0 and the post-baseline value is 0. The percent is the “count” divided by the is the number of NSAA items with a baseline score >0 and non-missing Week 52 value).

- Gain of function in Week 52 NSAA Items: For each of the 17 NSAA items, the number and percent of patients with a gain in function will be summarized. A patient is defined as having a gain in function if the baseline items score is 0 and the post-baseline value is >0 (i.e., a score of 1 or 2). Patients with a baseline item score of 1 or 2 or a missing Week 52 NSAA item value are excluded from the analysis (i.e., this analysis is based on the items with a baseline score of 0).

For each item, the percentages, odds ratio (with 95% CI), and a p-value comparing the treatment group difference in proportions will be presented.

For the Overall NSAA gain of function, the overall odds ratio, 95% CI, and p-value will be estimated from a generalized estimating equations (GEE) model with treatment and

NSAA item as class variables in the model, gain of function (i.e., a dichotomous variable) as the dependent variable, baseline item score as a covariate, and subject as the repeated term with an exchangeable working correlation matrix.

The patient count and percent of number of Week 52 NSAA items with a gain in function will be presented (i.e., the “count” is the number of NSAA items with a baseline score of 0 and the post-baseline value is >0. The percent is the “count” divided by the is the number of NSAA items with a baseline score of 0 and non-missing Week 52 value).

- NSAA Items: Change from Baseline: For each NSAA item at each scheduled visit, the change from baseline will be summarized and the two treatment groups will be compared using CMH test on change from baseline score controlling for baseline NSAA item score.

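### SAP 4.10.7 compares the NSAA change categories without covariates, and its five item-level GEE models omit the stratification variables that 4.2.4 says models adjust for

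*SAP*

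**What the plan says.** SAP 4.10.7 sets five improvement thresholds (at least 0 up to at least 4) and six decline thresholds (0 or less down to -5 or less) for the change in NSAA Total Score. It says: "The percentage of patients with a change from baseline in NSAA Total Score at Week 52 will be compared between the treatment groups". The test is given as "The difference between the treatment groups will be compared by a chi-square test", except for small counts, "in which case a Fisher's exact test will be used". Neither covariates nor strata are used. On the analysis set it says "These analyses will be performed on the FAP". It gives no rule for a boy in the FAP who has no Week 52 Total Score.

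The same section fits five overall item-level GEE models: increase, preservation, worsening, loss and gain of function. Each has treatment and item as class variables, with "baseline item score as a covariate, and subject as the repeated term with an exchangeable working correlation matrix". These analyses do state a missing-data rule. For increase in function it is: "Patients with a baseline item score of 2 or a missing Week 52 NSAA item value are excluded from the analysis". A separate CMH test of item change controls for baseline item score.

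SAP 4.2.4 says: "Statistical models will adjust for the stratification variables as covariates". The strata are age, time to stand, eteplirsen use and region. The FAP excludes boys on eteplirsen at randomization, so three strata matter here. The primary model in 4.10.1 contains all three (age and time to stand as continuous variables) plus baseline NSAA. For the continuous change scores, 4.10.6.1 adds: "Fifty imputed datasets will be created". SAP 4.10.6.2 creates the same number under the placebo-based assumption. Neither set is linked to the categories.

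**The concern.** The category and item analyses support the primary result by showing how many boys improve or decline by a given amount. The plan measures four baseline variables, randomises on three of them and uses all four in the primary model, then leaves all four out here. If they predict NSAA change, the supportive estimates are less precise than the data allow. The GEE models also sit awkwardly beside 4.2.4.

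A second, smaller gap is the denominator. FAP entry needs only one post-Baseline NSAA, so some boys will have no usable Week 52 total. If a programmer divides by the whole FAP, those boys count as not declined in the decline rows and as not improved in the improvement rows.

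**Working it through.** **1. The GEE models against 4.2.4.** Region, age and time to stand appear in none of the five. Baseline NSAA Total Score is also absent; it is not a stratification variable, so its omission is a loss of precision rather than a departure from 4.2.4. Baseline item score can be 0 or 1 in the increase model, and 1 or 2 in the preservation, worsening and loss models. In the gain model only items with baseline score 0 are eligible, so the covariate is constant, duplicates the intercept and adjusts for nothing.

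**2. The plan's own power figure (primary endpoint only).** Inputs from SAP 4.1: 126 boys, 2:1, difference 3.0, SD 4.8, 20% dropout, two-sided 0.05.
- Evaluable: 126 × 0.8 = 100.8, that is 67.2 and 33.6. Effect size: 3.0 / 4.8 = 0.625.
- 0.625 / √(1/67.2 + 1/33.6) = 0.625 / 0.2113 = 2.958. Power = Φ(2.958 − 1.960) = 84.1%, or 83.4% by the t distribution.

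The plan says about 80%. The gap is conservative and is not the issue here. No power is stated for the category tests.

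**3. The unadjusted category test.** Assume normal changes, placebo mean −3, active mean 0 and threshold −3 or less (cut at −2.5).
- Placebo: Φ(0.5/4.8) = 54.1%. Active: Φ(−2.5/4.8) = 30.1%. Difference: 24.0 points.
- Pooled rate: (54.1 + 2 × 30.1)/3 = 38.1%. Null SE = √(0.381 × 0.619 × (1/33.6 + 1/67.2)) = 0.1026. Alternative SE = √(0.541 × 0.459/33.6 + 0.301 × 0.699/67.2) = 0.1026.
- Power = Φ((0.240 − 1.96 × 0.1026)/0.1026) = 65%.

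**4. Gain from adjustment.** Simulation: 67 against 34 boys, 3,000 trials per setting, placebo mean −3 or −1, thresholds −1 and −3, one covariate standing for the set. The documents give no R-squared, so a range is shown.

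| Assumed R-squared | Chi-square/Fisher | Adjusted logistic | Gain (points) | ANCOVA on the score |
|---|---|---|---|---|
| 0 | 62–66% | 61–67% | about 0 | 83–84% |
| 0.1 | 62–66% | 64–69% | 2–4 | 86–88% |
| 0.2 | 62–66% | 66–72% | 4–6 | 90–91% |
| 0.3 | 61–66% | 68–75% | 7–10 | 93–94% |

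With four covariates sharing the R-squared (placebo mean −3, threshold −3, 4,000 trials each), the gains were about 0, 2, 5 and 9 points. The GEE models were not simulated.

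**5. Size.** In 3,000 null trials, rejection was 5.5% (chi-square/Fisher) and 6.2% (logistic likelihood ratio). The simulation error is √(0.05 × 0.95/3000) = 0.4 points. In 15,000 null trials, the logistic figure was 5.3% with one covariate and 6.3% with four, against 5.0% and 5.1% for chi-square/Fisher. The likelihood-ratio test is slightly liberal at this sample size, which accounts for a little of the gain.

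**6. The denominator.** Rates from step 3, with missingness unrelated to outcome.
- 20% missing in each arm, counted as not declined: 0.8 × 54.1 = 43.3% and 0.8 × 30.1 = 24.1%. The 24.0 points become 19.2.
- 30% placebo and 15% active missing (20% overall at 2:1): 0.70 × 54.1 = 37.9% and 0.85 × 30.1 = 25.6%. They become 12.3.
- Observed changes are integers, so at least 0 and −1 or less are complements and should show the same 24.0 points. With 30%/15% missing over the whole FAP, the first gives 0.85 × 54.1 − 0.70 × 30.1 = 24.9 and the second gives 0.70 × 69.9 − 0.85 × 45.9 = 9.9.

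**7. Imputed values.** SAP 4.10.6 rounds imputed NSAA changes to one decimal. An imputed −2.7 is not −3 or less, and an imputed −0.3 is neither at least 0 nor −1 or less. Thresholds need a rounding rule first.

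**The case against.** The planned test is valid without covariates, and no power is claimed for it. The same NSAA change is already analysed with full adjustment by MMRM and with imputation under two assumptions. A Kolmogorov–Smirnov test and the CMH item test add further support. Dichotomising costs more power than leaving out covariates (ANCOVA 83–84% against 62–66% at R-squared 0), and adjustment does not recover that. An adjusted odds ratio is also a conditional quantity and does not replace a difference in percentages. All of this stands, and it makes the point modest.

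Three stronger readings are tempting and are not supported:
- *The SAP ignores boys with no Week 52 score.* It is silent for the Total Score categories; exclusion is written only for the item analyses. Observed cases is the most coherent reading, given the neighbouring rules and the observed-case primary analysis. Table shells, which might settle it, are in a separate document.
- *Boys are censored for decline.* SAP 4.10 censors after corticosteroid start or treatment discontinuation. A link to decline is an inference.
- *The chi-square test contradicts 4.2.4.* That sentence concerns statistical models, so it reaches the GEE models only.

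Bias on the observed-case reading is also small. In a large simulation with 14–18% missing, concentrated in decliners, a true 22-point difference read as 21–22 with observed cases and 17 with the whole FAP.

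**Conclusion.** The point holds as a modest, inexpensive gain in precision and consistency. The category tests are unadjusted. The five GEE models omit the stratification variables despite 4.2.4, and one of them carries a covariate that cannot vary. Adjusting the category comparisons is worth about 0 points of power if the covariates are not prognostic, and 7 to 10 at R-squared 0.3. These figures rest on the SAP's SD of 4.8 and difference of 3.0, and on assumed placebo means and R-squared values. The gain for the GEE models has not been quantified.

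The unstated denominator is a clarification. It matters only if someone divides by the whole FAP; 24 points would then read as 19 under the stated assumptions. A reader might infer that the efficacy conclusion is at risk. It is not: these analyses are labelled supportive and lie outside the hierarchy in 4.2.5.

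**What to change.** In SAP 4.10.7:

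1. Add region, baseline age, baseline time to stand and baseline NSAA Total Score to the five overall GEE models. Drop baseline item score from the gain-of-function model.
2. For each Total Score threshold, add a logistic model with treatment and the same four covariates. Report a standardised risk difference or an adjusted odds ratio, with the variance method named in advance. Keep chi-square/Fisher as the descriptive comparison and for sparse categories.
3. State that the percentages use boys with an uncensored Week 52 Total Score, and show the number missing by arm.
4. As a sensitivity analysis, derive the categories from the existing MAR and placebo-based imputed datasets, rounding imputed changes to the nearest integer before applying thresholds, and combine by Rubin's rules.

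The cost is a few sentences and a little programming; no new data are needed. Rare categories will still need an exact or penalised method, and the likelihood-ratio test runs slightly above its nominal size with four covariates. These changes should be fixed before unblinding.
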